3.0: Study Design

3.1: Overview

This matched cohort study will compare adverse outcomes in women vaccinated in pregnancy to unvaccinated pregnant women. The primary analysis will draw the unvaccinated pregnant women from the pre-pandemic period, with supplementary analyses conducted with controls from the pandemic vaccination period. The matching process is detailed in section 3.6.

3.2: Study population

Pregnant women will be identified for inclusion in the matched cohort study through the COPS study database¹. The COPS study database includes all women aged 11 to 55 at the time of conception who were known to be pregnant in Scotland from 01 January 2015 to the present date. In the COPS database, pregnancies are followed-up from conception to the end of the puerperium (six weeks after end of pregnancy) for women and the end of the neonatal period (28 days following birth) for live born babies.

3.3: Study period

The matched cohort study will cover the time period 01 January 2015 to the date of data extraction for the analyses. There are three study periods referred to in this protocol, as follows:

- Pre-pandemic period (01 January 2015 to 29 February 2020)
- Pandemic pre-vaccination period (from 01 March 2020 to 07 December 2020; not included in the analyses described in this protocol)
- Pandemic vaccination period (from 08 December 2020 to date of data extraction)

Vaccinated individuals will have received any COVID-19 vaccine in the six weeks preceding conception or at any point between conception and the end of pregnancy between 08 December 2020 to the date of data extraction, and unvaccinated individuals will be identified from the pre-pandemic period (primary analysis) and the pandemic vaccination period (supplementary analyses 1 & 2).

3.4: Data Sources

This study will involve linkage and analysis of routinely collected electronic health records on maternal, pregnancy and neonatal outcomes, vaccination data and other covariates of interest.

¹ Stock SJ, McAllister D, Vasileiou E, *et al.* COVID-19 in Pregnancy in Scotland (COPS): protocol for an observational study using linked Scottish national data. *BMJ Open* 2020;**10**:e042813. doi: 10.1136/bmjopen-2020-042813. Available from: [COVID-19 in Pregnancy in Scotland \(COPS\): protocol for an observational study using linked Scottish national data | BMJ Open](#)

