For the matched cohort study, the primary comparison for each outcome will be between women vaccinated in the six weeks preceding conception or up to the end of the outcome-specific exposure period within pregnancy and unvaccinated pregnant women from the pre-pandemic period. Only women who had been followed-up to the end of the outcome-specific follow-up period on the 29 February 2020 are eligible to be controls for that outcome analysis. Women who have COVID-19 infection from six weeks preconception up to the end of the outcome-specific follow-up period will

not be eligible for inclusion in the vaccinated group for this primary analysis. Each individual in the pregnant vaccinated cohort will be matched to three individual unvaccinated pregnant controls, if possible⁵. Different pregnancies from a single woman can be matched to different cases, and if a case had a pregnancy in the pre-pandemic period, that pregnancy is a valid control, as long as the woman is not matched to herself. Here the assumption is that pregnancies are independent. A sensitivity analysis will be conducted, removing women who are vaccinated in the six weeks preconception – and her controls – from the analysis.

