*Note that only women who have been followed-up to the end of the outcome-specific follow-up period at the end of each study period (i.e. 29 February 2020 for pre-pandemic controls and data of data extraction for pandemic controls) are eligible to be controls for a given outcome analysis.

3.7: Power calculation for matched cohort

It is estimated that by the end of 2021, full outcome and follow-up data will be available for approximately 5,000 vaccinated pregnant women, and by end of 2022, data available for 10,000 vaccinated pregnant women⁶.

Outcomes can be grouped as frequent (risk approximately 10%), moderate (approximately 3%), and rare (approximately 0.5%). Risk estimates for each adverse outcome are provided in Table 2. Based on these estimates and assumptions, with the relative risk of an event occurring post-vaccination set at 0.5, 1.2 and 2.0, and with statistical significance set at 0.05 and 0.01; power calculations for the various scenarios were calculated and are shown in Table 6. The power to detect a relative risk of 0.5, based on 5000 vaccinated pregnant woman against 15000 controls (ratio 1:3), when estimated

⁶ Personal communication with [name], July 2021.

adverse event occurrence is 0.5%, is 94%. This means that the study has a 94% chance of having a p-value of less than 5% (a statistically significant result and strong evidence against the null hypothesis) if there is really a difference in risk between vaccinated and unvaccinated women.

If the statistical power is low, the study sample size may be too small to detect any differences (i.e. under-powered) and therefore null results will need to be interpreted with caution. By convention, 80% is an acceptable level of power. It is acknowledged that the study may be under-powered to identify rarer outcomes.

Table 6: Power calculations scenarios

Cases	Controls	Estimated risk	Relative risk	Power %
5000	15000	0.50%	0.5	94
			1.2	10
			2.0	66
		3.00%	0.5	100
			1.2	45
			2.0	100
		10.00%	0.5	100
			1.2	94
			2.0	100
10000	30000	0.50%	0.5	100
			1.2	17
			2.0	94
		3.00%	0.5	100
			1.2	75
			2.0	100
		10.00%	0.5	100
			1.2	100
			2.0	100

4.0: Data Analyses

4.3: Descriptive analyses

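### Three controls per vaccinated woman is a defensible choice, but in the pre-pandemic primary analysis it gives up some precision on rare outcomes at almost no saving

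*Protocol*

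**What the plan says.** Section 3.6 of the Protocol states that each woman in the vaccinated cohort "will be matched to three individual unvaccinated pregnant controls, if possible", with a footnote to an earlier cohort study of vaccination in pregnancy. Table 5 repeats the aim of three controls for the primary analysis and both supplementary analyses.

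The primary controls come from the pre-pandemic period, 01 January 2015 to 29 February 2020 (62 months). Section 3.2 says the source database includes "all women aged 11 to 55 at the time of conception who were known to be pregnant in Scotland from 01 January 2015" onwards. Matching is on maternal age (within 1 year), gestational week and quarter of conception. Age and gestation may be relaxed at the tails.

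Section 3.7 bases its power figures on 1:3, with 5,000 or 10,000 vaccinated women. It adds: "It is acknowledged that the study may be under-powered to identify rarer outcomes". Section 5.0 repeats this as a limitation. Section 4.5 lists two further analyses that will be considered: a comparison of observed outcomes with those predicted from all pre-pandemic data, and a nested case-control study of rarer outcomes if signals appear.

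**The concern.** A small fixed number of controls is usual where each control has to be recruited, sampled or abstracted. Here the primary controls are existing linked records, so a fourth or tenth control costs little beyond computing. The only support given for three is the cited earlier study.

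This matters most for rare outcomes such as venous thromboembolism and neonatal death. A safety study that finds no association reassures through its upper confidence limit, and that limit is wider than it needs to be if eligible controls are left unused.

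**Working it through.** **Inputs.** Vaccinated women n = 5,000 or 10,000 and k = 3 controls each (section 3.7, Table 6). Control risks p0 from Table 2: venous thromboembolism 0.15%, neonatal death 0.2%, stillbirth 0.4%. Relative risks: "with the relative risk of an event occurring post-vaccination set at 0.5, 1.2 and 2.0". RR 1.5 is added here as an intermediate value and is not in the plan. Sidedness is not stated, so two-sided 0.05 is assumed.

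**Power formula** (pooled normal approximation). With p1 = RR × p0 and p̄ = (p1 + k·p0)/(1 + k):

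- s0 = √[p̄(1 − p̄)(1/n + 1/(kn))]
- s1 = √[p1(1 − p1)/n + p0(1 − p0)/(kn)]
- power = Φ[(|p1 − p0| − 1.96·s0)/s1]

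**The plan's own figures.** For 0.5% risk and 5,000 against 15,000, Table 6 prints 94, 10 and 66% for RR 0.5, 1.2 and 2.0. Applying the relative risks as labelled gives 66.5, 14.4 and 94.8%. Setting the vaccinated risk to p0/RR gives 94.8, 10.1 and 66.5%, and this inversion reproduces all 18 cells of Table 6 within 2 points. That is a separate and more serious problem. The figures below apply the relative risk as labelled, so they do not share a baseline with Table 6.

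**Precision under the null.** For a rare outcome, SE(log RR) is proportional to √(1 + 1/k).

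| k | √(1 + 1/k) | SE relative to 1:3 | Share of maximum information, k/(k + 1) |
|---|---|---|---|
| 3 | 1.155 | 1 | 75% |
| 5 | 1.095 | 0.949 | 83% |
| 10 | 1.049 | 0.908 | 91% |
| unlimited | 1.000 | 0.866 | 100% |

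**Expected upper 95% limit, venous thromboembolism, 5,000 vaccinated, true RR 1.** Expected vaccinated events are 5,000 × 0.0015 = 7.5.

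- 1:3: SE = √(1/7.5 + 1/22.5) = 0.4216; limit = exp(1.96 × 0.4216) ≈ 2.29
- 1:10: SE = √(1/7.5 + 1/75) = 0.3830; limit = exp(1.96 × 0.3830) ≈ 2.12

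**Power, worked case** (venous thromboembolism, RR 2.0, n = 5,000).

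- 1:3: p̄ = 0.001875, s0 = 0.0007064, s1 = 0.0008355; (0.0015 − 0.0013846)/0.0008355 = 0.138, so power is 55.5%
- 1:10: p̄ = 0.001636, s0 = 0.0005995, s1 = 0.0007926; (0.0015 − 0.0011750)/0.0007926 = 0.410, so power is 65.9%

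**Power (%) by ratio.**

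| Outcome, RR, n | 1:3 | 1:5 | 1:10 | Unlimited |
|---|---|---|---|---|
| Venous thromboembolism, 2.0, 5,000 | 55.5 | 61.2 | 65.9 | 71.0 |
| Venous thromboembolism, 2.0, 10,000 | 81.1 | 85.3 | 88.4 | 91.2 |
| Neonatal death, 2.0, 5,000 | 66.2 | 71.6 | 75.9 | 80.3 |
| Neonatal death, 2.0, 10,000 | 89.9 | 92.7 | 94.6 | 96.3 |
| Stillbirth, 2.0, 5,000 | 90.0 | 92.8 | 94.7 | 96.3 |
| Stillbirth, 1.5, 10,000 | 71.5 | 76.3 | 80.1 | 83.8 |

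**Controls needed if none is reused.** For 5,000 vaccinated women: 15,000 at 1:3, 25,000 at 1:5 and 50,000 at 1:10. For 10,000: 30,000, 50,000 and 100,000. The Protocol gives neither the size of the matchable pool nor a rule on reuse, so the 1:5 and 1:10 columns serve as a range.

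**The case against.** The strongest reply is that nothing here is misstated or unworkable. Three controls follow a cited precedent and already capture three quarters of the attainable information under the null. The main constraint is the number of vaccinated women and their events. In the 5,000-woman scenarios at 0.15%, 0.2% and 0.5% risk with the plan's relative risks, no ratio up to 1:20 lifts an under-powered case to the plan's 80% benchmark. Where power is already high, as for a doubling of stillbirth, little is gained. All of this stands.

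Feasibility also counts. Matching on age, gestational week and quarter may leave some strata short, and Section 3.6 itself expects fewer candidates at the tails of maternal age. More controls would bring in more repeat pregnancies, which the plan treats as independent, so the gain may be overstated. This stands as a reason to treat the 1:10 figures as best case. It does not defeat a variable ratio, because sparse strata would simply receive fewer controls, and the plan already accepts fewer than three.

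A reader might infer that the plan ignores the rest of the pre-pandemic data. Section 4.5 does not support that, since it names an analysis using all of it. But that analysis is only to be considered, and the nested case-control study depends on a signal, so neither secures extra precision for a null result.

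Changing the ratio in the primary analysis alone would also break its symmetry with the supplementary analyses. Reporting the 1:3 result as well meets this.

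**Conclusion.** This is an optional, low-cost improvement and not a defect. With existing records as controls, the 1:3 target gives up about 5% (against 1:5) to 9% (against 1:10) in the null standard error. For a doubling of a 0.15–0.2% risk with 5,000 vaccinated women, that is about 5 to 10 points of power.

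It would be tempting to conclude that the three-control limit is why rare outcomes are under-powered. The figures do not support that: with 5,000 vaccinated women, a doubling of venous thromboembolism reaches only about 71% power with unlimited controls. Among the scenarios tabulated above, only stillbirth at RR 1.5 with 10,000 women crosses 80% between 1:3 and 1:10, and only just.

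The conclusion assumes two-sided 0.05, the background risks in Table 2 and enough matchable pregnancies. The calculations ignore matching, covariate adjustment, the multiplicity correction and repeat pregnancies. More historical controls do nothing to reduce bias from changes between the pre-pandemic and pandemic periods.

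**What to change.** For the primary pre-pandemic analysis only:

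1. Assign up to three controls per vaccinated woman as planned. Then fill to a stated maximum of between five and ten from the remaining eligible pregnancies, within the unrelaxed age, gestation and quarter criteria.
2. Report the distribution of controls obtained per vaccinated woman, and the size of the matchable pool.
3. Keep the models in section 4.4: conditional logistic regression, and the conditional multinomial model with the matching factors for stillbirth and the other competing pregnancy outcomes.
4. Weight crude control risks by matched-set size (each control in a set of m counts 1/m), so that the descriptive tables stay comparable.
5. Show the 1:3 result alongside, for comparison with the supplementary analyses.

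If the team prefers to keep 1:3, one sentence saying why three suffices would settle the point. The cost of the change is more computing, uneven set sizes and the weighting of descriptive risks.

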Pregnant women will be identified through the COPS² study database if they appear on one or more of the data sources listed for the identification of pregnant women in Table 1.

Table 1: Overview of data sources used for analysis

Data	Data source

Datasets required to identify pregnant women in the general population and associated pregnancy start and end dates:
	
 • New national data return developed as part of the response to the COVID-19 pandemic providing information on women booking for antenatal care with NHS maternity services: for identification of women with ongoing pregnancies in near real-time (all other records that identify end of pregnancy events) • GP consultation data: for identification of women with early miscarriage or ectopic pregnancy not managed in hospitals • Scottish Morbidity Record (SMR) 01: for identification of women with early miscarriage or ectopic pregnancy managed in hospitals • Termination of pregnancy statutory notifications (AAS records) • SMR 02: for identification of later miscarriage, stillbirth, and live births managed in hospital (and some home births) • National Records of Scotland (NRS) statutory stillbirth registrations • National Records of Scotland (NRS) statutory live birth registrations • New national data return developed as part of the response to the COVID-19 pandemic providing information on live births notified by maternity services to NHS Board child health administrative departments: for near real-time access to data that allows intergenerational linkage of records relating to mothers and their babies. 
Note that this is already established as part of the COPS study and methodology is set out in the Protocol for estimating the number of COVID-19 vaccinations delivered to pregnant women in Scotland and for describing the uptake and coverage of vaccination in the pregnant population.

Datasets required to identify characteristics of pregnant population
	
 • Covariates of interest include: Maternal age, deprivation score, urban/rurality score, ethnicity, pre-pregnancy clinical vulnerability exc diabetes, diabetes, BMI, smoking status, and linked PCR test data to capture confirmed cases of COVID-19 infection. 
Note that all are available through the COPS study database.

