Longer term child outcomes, including immune function and infection, and neurodevelopment, will be addressed in future work as required.

Other adverse outcomes that are not specific to pregnant women, will be investigated separately for the whole population as part of wider adverse events monitoring in Scotland. If these analyses suggest any signals in the pregnant population, those outcomes would be investigated in the pregnant population using the COPS data infrastructure, as required.

Table 2: Maternal, pregnancy and neonatal outcome measures for monitoring of safety of COVID-19 vaccination in pregnancy

Outcome measure	Definition	Primary or secondary outcome?	Clean window requirement to identify incident cases	Timing of vaccination to be included	Post vaccination risk period to be examined	Estimated background risk of outcome (%)
Maternal outcomes						
Hypertensive disorders of pregnancy	See ICD10 code list. Note that hypertensive disorders can only be diagnosed at >20 weeks.	Primary	No prior record in this pregnancy	Any	Up to E plus PP	10.0
Venous thromboembolism	See ICD10 code list	Primary	No prior record in this pregnancy	Any	Up to E plus PP	0.15
Pregnancy-related bleeding	See ICD10 code list	Primary	No prior record in this pregnancy	Any	Up to E plus PP	30.0 (for postpartum haemorrhage)
ICU admission or death (any cause)	ICU admission as identified on SICSAG record Death from any cause	Primary	None (but exploration to be undertaken of reasons for any pre-vaccination ICU admission where these are documented)	Any	Up to E plus PP	Unknown
Pregnancy outcomes						
Miscarriage	Miscarriage at <24 completed weeks gestation	Primary	None	Up to 23w+6d gestation	Up to 23+6 gestation	10.0 – 20.0

• First trimester miscarriage	Miscarriage at <14 completed weeks gestation	Secondary	None	Up to 13+6 gestation	Up to 13+6 gestation	Unknown
• Second trimester miscarriage	Miscarriage at 14-<24 completed weeks gestation	Secondary	None	Up to 23+6 gestation	14+0 to 23+6 gestation	Unknown
Ectopic pregnancy	Ectopic pregnancy ending at any gestation	Primary	None	Up to 2+6 gestation	Up to E	1.0
Stillbirth	Spontaneous fetal loss at ≥24 completed weeks gestation Any cause of fetal death Losses related to termination of pregnancy excluded	Primary	None	Any	24+0 to E	0.4
Baby outcomes (live births only unless otherwise stated)						

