With the pre-pandemic period being used as the baseline, there is an assumption that the pandemic has not substantially affected the outcomes of interest through, for example, changes in engagement and provision of maternity services. To investigate this, a supplementary analysis will be conducted with pregnant unvaccinated controls from the pandemic vaccination period (from 08 December 2020 to date of data extraction). In this supplementary analysis, we will exclude women (from both the vaccinated and unvaccinated group) who had any record of COVID-19 infection from six weeks preconception to the end of the outcome-specific follow-up period. However, given that there is potential for vaccination to impact on maternal, pregnancy and neonatal outcomes by changing the risks of acquiring COVID-19 and experiencing severe illness, we will also conduct a second supplementary analysis with pregnant unvaccinated controls from the pandemic. In this, we will retain both vaccinated and unvaccinated women with a confirmed record of COVID-19 infection during pregnancy and preceding the end of the outcome-specific follow-up period. For both these supplementary analyses, women who were vaccinated >6 weeks pre-conception will be included in the control group (as not vaccinated in pregnancy), however sensitivity analyses (if sample size permits) will be conducted to investigate any differences between pairs where the control is completely unvaccinated versus pairs where the control received vaccination >6 weeks pre-conception (e.g. vaccinated pre-‘pregnancy’). Additional supplementary analyses removing women who are vaccinated in the six weeks preconception will be considered for the analyses using women from the pandemic period as controls, if we observe an impact of removing these women in the primary analysis using pre-pandemic controls.

Maternal and gestational age are known to be important risk factors for adverse events in pregnancy (e.g. miscarriage strongly influenced by maternal age). Consequently, the cohorts will be matched by maternal age (± 1 years but relaxed (i.e. possibly $\pm >1$ year) at the tails of maternal age distribution as fewer individuals available for matching), and gestational age (exact match, i.e. same week however allow for relaxation of this at the tails of the gestation distribution).

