In addition, vaccinated pregnant women will also be matched by season of conception (quarter) to historical controls from the pandemic and pre-pandemic periods due to the seasonality of some outcomes. It is not necessary to do this for contemporary controls (from the pandemic vaccination period) as those pairs will be matched by calendar date (i.e. matching a vaccinated woman by maternal and gestational age, on the day of vaccination to a control of the same maternal and gestation age, on the same date).

For comparisons between vaccinated and unvaccinated matched individuals, the index date (reference point for matching maternal and gestational age, and season of gestation for analyses involving controls from historical periods only) will be the date of vaccination.

⁵ Donegan K, King B, Bryan P. Safety of pertussis vaccination in pregnant women in UK: observational study BMJ 2014; 349:g4219 doi:10.1136/bmj.g4219. Available from: <https://www.bmj.com/content/349/bmj.g4219>

The matching strategy for each of the three analyses is shown in Table 5.

Table 5: Matching strategy for each analysis of the matched cohort study

Analysis	Time period for control group*	Matched three controls to each case by:	Notes
Primary analysis	Pre-pandemic period (01 January 2015 to 29 February 2020)	
 Maternal age Gestational age Season of conception (quarter) 	
 Aim to match to three unvaccinated controls Maternal age matched by ± 1 year but relaxed at tails of maternal age distribution Gestational age matched by same week but relaxed at tails of the gestation distribution
Supplementary analysis 1	Pandemic vaccination period (from 08 December 2020 to date of data extraction), excluding cases and controls with confirmed COVID-19 between six weeks preconception to end of outcome-specific follow-up period	
 Maternal age Gestational age 	
Supplementary analysis 2	Pandemic vaccination period (from 08 December 2020 to date of data extraction), including cases and controls with confirmed COVID-19 between six weeks preconception to end of outcome-specific follow-up period	
 Maternal age Gestational age 	

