First, a model with no covariates will be fitted to calculate the unadjusted OR for the association between vaccination status and each outcomes of interest. Subsequently, we will calculate an adjusted OR for the association between vaccination status and each outcomes of interest, by adding all covariates to the model (Table 4). P-values and confidence intervals will be reported for all models. For some rarer outcomes, we will adjust our modelling approach as required (e.g. re-classification of groupings or removing insignificant covariates). Covariate pairs will be assessed for collinearity before adding to the model. For any covariate pairs that are highly correlated, only the covariate which has the biggest impact on the association between the exposure and outcome will be included in the model.

As previously described (section 3.5.2), analyses will be conducted first looking at the association between having any vaccination and outcomes, and then in sub-group analyses stratified by vaccine classes and individual vaccine types;

- Vaccine type: Pfizer, AstraZeneca, Moderna, Janssen
- Vaccine group: Pfizer and Moderna (mRNA); AstraZeneca and Janssen ((adeno)virus vector)
- Number of vaccine doses

Our main analyses will include all pregnancies/births, regardless of whether there is evidence that it was singleton or multiple, with sensitivity analyses conducted restricting to only pregnancies/births where there was no evidence it was a multiple. We often do not know whether pregnancies which end early (e.g. due to miscarriage) were singleton or multiple, hence the decision to only include pregnancies with *no evidence* of being a multiple in these sensitivity analyses.

4.5: Additional analyses

There are two further analyses that may subsequently be conducted to assess the association between vaccination and adverse outcomes, specifically:

1. We will consider using all data from the pre-pandemic period to predict the expected number of outcomes among the vaccinated pregnant women, and compare this predicted number to the observed number within the vaccinated group of women.
2. For rarer outcomes (e.g. for congenital anomalies, microcephaly), we will consider a nested case control study if signals are identified in this present matched cohort analysis but wide confidence intervals due to the small number of events negate any meaningful conclusions. This design maximises power to assess any association between vaccination and these rare outcomes.

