Appendix 3: Measuring the impact of infection on adverse pregnancy, maternal and neonatal outcomes

Noted below are amendments required to the study design to examine the impact of COVID-19 infection (rather than vaccination) on adverse pregnancy, maternal and neonatal outcomes.

Study population	Same study population as for vaccination exposure (described in Section 3.2).
Study period	
This matched cohort study will cover the time period 01 January 2015 to the date of data extraction for the analyses, with the exclusion of the time period when testing for COVID-19 infection was not widespread:
 
 • Pre-pandemic period (01 January 2015 to 29 February 2020) • Pandemic pre-widespread testing period (from 01 March 2020 to 17 May 2020; not included in the analyses on impact of infection on outcomes) • Pandemic widespread testing period (from 18 May 2020 to date of data extraction)
Exposure	
The primary exposure to be investigated in the analyses is any confirmed COVID-19 (indicated by positive PCR test for SARS-CoV-2 virus) from six weeks preconception to the end of an outcome-specific exposure period within pregnancy (Yes/No). The date of onset of COVID-19 is defined as the date the woman's first positive PCR sample was taken. Subsequent positive PCRs within 90 days of an index positive result are discounted. Any positive test taken >90days following the first positive sample is taken as indicating a second infection, and so on.

Outcomes	
The timing of COVID-19 infection for each outcome (ie the outcome specific exposure period) is the same as is included for vaccination (see Table 2).
 
So, for example, for the outcome of miscarriage, we will include women in the COVID-19 infection group if they have a confirmed COVID-19 diagnosis between six weeks preconception and 23⁺⁶ weeks of gestation.

Covariates	Same covariates as for vaccination exposure (described in Section 4).

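### Supplementary analysis 2 keeps infections that preceded vaccination and neither matches on them nor lists them for adjustment, leaving a measured baseline confounder uncontrolled; the direction of bias is unknown

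*Protocol*

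**What the plan says.** Section 3.6 of the Protocol explains supplementary analysis 2 by the possibility that vaccination alters outcomes "by changing the risks of acquiring COVID-19 and experiencing severe illness". For that reason, "we will retain both vaccinated and unvaccinated women with a confirmed record of COVID-19 infection during pregnancy"; the only other limit stated there is that the infection comes before follow-up for the outcome ends. Table 5 describes the same analysis as "including cases and controls with confirmed COVID-19 between six weeks preconception to end of outcome-specific follow-up period". The text therefore starts the window at pregnancy and the table starts it six weeks before conception. Neither divides it at the index date, which Section 3.6 sets as the date of vaccination.

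Contemporary controls are matched on maternal age, gestational age and calendar date (Section 3.6, Table 5). The adjusted odds ratio is obtained "by adding all covariates to the model (Table 4"). Table 4 lists deprivation, urban-rural status, ethnicity, clinical vulnerability, diabetes, BMI and smoking. It has no infection variable. Table 1, however, ends its list of covariates with "and linked PCR test data to capture confirmed cases of COVID-19 infection".

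For ICU admission or death, the clean-window entry in Table 2 is "None (but exploration to be undertaken of reasons for any pre-vaccination ICU admission where these are documented").

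Appendix 3, on infection as the exposure, borrows the adjustment set: "Same covariates as for vaccination exposure (described in Section 4"). Its Match 3 includes vaccinated women in both groups.

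**The concern.** The stated purpose covers only infection that vaccination could prevent or attenuate, that is, infection after the index date. Infection between six weeks before conception and the index date is a baseline characteristic. It may affect the outcome, and it may be related to whether a woman was vaccinated on that date. If it differs between the groups, it confounds the comparison.

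Section 3.5.3 uses this reasoning to adjust for gestational diabetes, citing its effect on uptake and its association with outcomes. Prior infection is linked and available, but it does not reach the model list.

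Supplementary analysis 2 is the only one of the three analyses in Table 5 that keeps infected vaccinated women, so it is the only one that can show a net effect including any protection against COVID-19. As specified, that net effect is mixed with differences in infection that existed before vaccination. ICU admission or death is the most exposed outcome: it is closely tied to acute illness, and no clean window removes women already in critical care on the matching date.

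**Working it through.** **Is pre-index infection controlled anywhere in supplementary analysis 2?**

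- Eligibility: no. Infected women are kept in both groups from six weeks before conception (Table 5).
- Matching: no. Only maternal age, gestational age and calendar date are used.
- Adjustment: no under Section 4.4, which points to Table 4. Table 1 names infection as a covariate, so the two tables disagree.

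**How large could the bias be?** The Protocol gives no figure to reproduce. It states no infection prevalence, and Table 2 gives the background risk of ICU admission or death as unknown. All inputs below are assumptions:

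- p1, p0: the share infected before the index date among vaccinated women and controls;
- R: the risk ratio for the outcome given that infection;
- no true vaccine effect.

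Spurious risk ratio = (1 + p1(R − 1)) / (1 + p0(R − 1)).

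| R | p1 0.5%, p0 2% | p1 1%, p0 4% |
|---|---|---|
| 1.5 | 1.0025/1.010 = 0.993 | 1.005/1.020 = 0.985 |
| 2 | 1.005/1.020 = 0.985 | 1.010/1.040 = 0.971 |
| 10 | 1.045/1.180 = 0.886 | 1.090/1.360 = 0.801 |
| 30 | 1.145/1.580 = 0.725 | 1.290/2.160 = 0.597 |

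The Protocol reports odds ratios. At baseline risks of 0.1% to 0.3%, the odds ratio agrees with these values to within about 0.001 (for example 0.885 at R = 10 in the first column).

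**Does the direction hold?** Only under the assumed imbalance. Take 2% infected among vaccinated women and 1% among controls:

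- R = 5: 1.08/1.04 = 1.04
- R = 10: 1.18/1.09 = 1.08
- R = 20: 1.38/1.19 = 1.16
- R = 50: 1.98/1.49 = 1.33

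The vaccine now looks harmful. If past infection halves later risk (R = 0.5) and controls are the more infected group (2% versus 0.5%), the ratio is 0.9975/0.990 = 1.01.

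**Do the large values of R apply to everyone in the window?** Probably not. The window includes recovered women, whereas 10- or 30-fold risks are plausible only for acute infection. Suppose that a quarter of the 2% of controls are acutely infected (0.5%), that recovered women carry no excess risk, and that no vaccinated woman is acutely infected:

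- R = 10: 1/(1 + 0.005 × 9) = 1/1.045 = 0.96
- R = 30: 1/(1 + 0.005 × 29) = 1/1.145 = 0.87

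The corresponding values in the table are 0.89 and 0.73.

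**Does the fix work?** Excluding pre-index infection sets p1 = p0 = 0, and the ratio is 1.00. Comparing women of the same infection status also gives 1.00. This holds within the simple model only.

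**The case against.** A reader might infer that the analysis will make the vaccine look protective because acutely infected women do not attend for vaccination. That is plausible, but the Protocol does not say it. Prior infection could also be commoner among vaccinated women. Section 3.5.2 notes that frontline health or care workers were prominent among early recipients of one vaccine, and more prior infection in that group is a conceivable inference, though not a documented one. The direction must be left open.

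A reader might also infer that infection is never adjusted for. Table 1 prevents so firm a statement. What can be said is that the list Section 4.4 sends to the model omits it and that the two tables conflict. An analysis plan not seen here might settle this, but the Protocol itself fixes the list.

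On ICU admission, the risk-period column of Table 2 is headed as post-vaccination, so it is not established that an admission beginning before the index date would be counted. Table 2 also promises to explore the reasons for earlier admissions, and Section 4.3 plans plots of time from vaccination or matching to outcome, which could reveal early clustering. These steps may expose a problem, but they do not correct the estimate.

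The consequence is limited. The primary analysis excludes infected vaccinated women and uses pre-pandemic controls, and supplementary analysis 1 excludes infection from both groups. Neither can stand in for analysis 2 on the net effect, because both also remove vaccinated women infected after vaccination. The general caveat in Section 5.0 concerns unmeasured confounding, whereas this factor is measured.

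**Conclusion.** The point holds as a gap in one supplementary analysis. As written, supplementary analysis 2 leaves a measured pre-exposure factor uncontrolled, and its stated purpose does not justify doing so.

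Under the assumed prevalences, the bias is about 1-3% for outcomes that infection raises 1.5- to 2-fold, which is minor. It could be material only for outcomes closely tied to acute COVID-19, chiefly ICU admission or death. There the illustrative ratio ranges from 0.96 down to 0.60, depending on prevalence, on R (10 or 30) and on how many infections are acute. It exceeds 1 if vaccinated women are the more infected group. The lowest values apply acute-illness risk to the whole window and should be read as extremes. None of these sizes can be derived from the Protocol.

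The documents do not support a claim of certain protective bias, or any claim that the primary analysis or supplementary analysis 1 is affected.

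**What to change.** 1. Reconcile Tables 1 and 4. For supplementary analysis 2, add confirmed infection between six weeks before conception and the index date as a covariate or matching factor, ideally split into recent and earlier infection. Alternatively, exclude such women from both groups.
2. Leave infection after the index date unadjusted, since it is the pathway this analysis is meant to retain.
3. Align the start of the infection window between the text of Section 3.6 and Table 5.
4. For ICU admission or death, count only admissions starting after the index date, and exclude women in critical care on that date.
5. As a separate, secondary point, add vaccination status on the date of infection to the matching or covariates for Match 3 in Appendix 3. Match 3 includes vaccinated women but borrows a covariate list with no vaccination variable. Match 2 excludes women vaccinated from six weeks before conception to the end of follow-up from both groups, and Match 1 excludes them from its exposed group and takes its controls from before the pandemic, so the gap is confined to Match 3.

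The cost is wording plus one covariate or filter from PCR data already linked. If exclusion is chosen, previously infected women leave the analysis. The Protocol does not say how many that would be.
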